## OBJECTIVES AND HYPOTHESIS:

The overall aim of the present study is to prospectively investigate the impact of two maintenance CNI immunosuppressive regimens (both prednisone-free, with MMF) on subpopulations of T and B cells and alloreactive T cells as well as on renal allograft function at week 2, 3 months and 12 months post-transplantation.

[figure not shown]
1. To compare renal toxicity of once-daily LCP-Tacrolimus/Envarsus XR vs. twice/day Tacrolimus by measured acute kidney injury markers.
2. To compare the effect on T and B cell subpopulations of once-daily LCP-Tacrolimus/Envarsus XR vs. twice /day Tacrolimus. Specific studies to include prospective, serial flow cytometric analysis of T and B cell subpopulations, as well as high throughput sequencing T cell receptor repertoire analysis monitoring for presence or absence of donor-reactive T cells.

Our hypothesis is that that more consistent exposure with LCP-Tacrolimus/Envarsus® XR avoiding under immunosuppression will prevent the emergence of alloreactive T cells, development of effector memory T cells, and a reduced incidence of immunologic allograft injury. We also posit that avoidance of the peaks associated with conventional twice daily tacrolimus will spare the renal allograft from drug induced nephrotoxicity.

## BACKGROUND:

Kidney transplantation is the treatment of choice for most patients with end-stage renal disease. Lifelong immunosuppressive therapies are required to prevent organ rejection. However, long term exposure to immunosuppressive therapy after kidney transplantation can place patients at risk for multiple adverse events. The optimal immunosuppressive therapy is not well established. Tacrolimus, a calcineurin inhibitor (CNI) is highly effective in preventing acute rejection after organ transplantation (2). It is used as part of the immunosuppression regimen for the majority of kidney and liver transplant recipients (3). However, treatment with current formulation of Tacrolimus generates high peaks and low troughs in drug concentrations in the blood. It is known that high exposure to CNI is associated with renal toxicities and adverse events (4). New once-daily dosage formulations are now developed with the hope of minimizing side effects while maintaining excellent outcomes (5-8).

LCP-Tacrolimus/Envarsus® XR, a new once-daily formulation of tacrolimus, was approved by the

*Northwestern University Feinberg School of Medicine:* Extended-Release Tacrolimus Vs. Twice-Daily Tacrolimus

FDA in 2015 for conversion from twice-daily tacrolimus in kidney transplant recipients. It is a prolonged-release tacrolimus formulation, utilizing a MeltDose drug delivery technology designed to improve the bioavailability of drugs with low water solubility (1). Recent clinical data demonstrated that once-daily LCP-Tacro/Envarsus XR has improved pharmacokinetic bioavailability, rapid achievement of therapeutic trough levels, less fluctuation and swing in whole blood concentration, non-inferior efficacy and similar safety, with lower tacrolimus dose than other tacrolimus formulations (1, 9-13). (**Figure1**).

## **INCLUSION AND EXCLUSION CRITERIA:**

The target population is adult recipients of immediately functioning living and deceased donor renal allografts. Immediate function will be defined as the absence of the need for hemodialysis in the first week following renal transplantation.

### **Inclusion Criteria:**

1. Patients who are males or females aged 18-65 years.
2. Donors aged 18-65 years.
3. No prior organ transplant
4. Patients who are single-organ recipients (kidney only).
5. Women who are of childbearing potential must have a negative serum pregnancy test before transplantation and agree to use a medically acceptable method of contraception throughout the treatment period.
6. Subject (recipient) is able to understand the consent form and give written informed consent

### **Exclusion Criteria**

1. Delayed graft function (please see above).
2. Known sensitivity or contraindication to alemtuzumab, Envarsus® XR, tacrolimus or MMF.
3. Use of the following induction medications: basiliximab and rituximab.
4. Patient with significant or active infection.
5. Patients with a positive flow cytometric crossmatch using donor lymphocytes and recipient serum.
6. Patients with PRA > 40%
7. Patients with current or historic donor specific antibodies
8. Body Mass Index (BMI) of < 18 or > 35
9. Patients who are pregnant or nursing mothers.
10. Patients whose life expectancy is severely limited by diseases other than renal disease.
11. Ongoing active substance abuse, drug or alcohol.
12. Major ongoing psychiatric illness or recent history of noncompliance.
13. Significant cardiovascular disease (e.g.):
  - a. Significant non-correctable coronary artery disease;
  - b. Ejection fraction below 30%;
  - c. History of recent myocardial infarction.
14. Malignancy within 3 years, excluding non-melanoma skin cancers.
15. Serologic evidence of infection with HIV or HBVs-Ag positive.
16. Patients with a screening/baseline total white blood cell count < 4,000/mm^3; platelet count < 100,000/mm^3; triglyceride > 400 mg/dl; total cholesterol > 300 mg/dl.
17. Investigational drug within 30 days prior to transplant surgery.
18. Anti-T cell therapy within 30 days prior to transplant surgery.

*Northwestern University Feinberg School of Medicine:* Extended-Release Tacrolimus Vs. Twice-Daily Tacrolimus

19. Diagnosis of atypical-Hemolytic Uremic Syndrome (aHUS).
20. Subjects transplanted with a Hepatitis C NAT-positive kidney.

## **NUMBER OF PARTICIPANTS:**

Prospective randomized single center open label study of 2 groups of kidney transplant patients

- Group 1 : standard of care (SOC) control group will receive tacrolimus twice-daily (n=25)
- Group 2 : LCP-Tacro/Envirox® XR group will receive LCPT tablets once daily (n=25)

## **RECRUITMENT METHODS:**

The investigators will recruit patients in a manner that is sensitive to the inclusion of women and members of minority groups into this study. The renal failure population awaiting transplantation on the participating program waiting lists is representative of the renal failure population in general. Subjects will be recruited from the patients who present themselves to Northwestern University, Kovler Organ Transplantation Clinic, located in [name].

### **Subject Information and Consent**

Prior to any testing under this protocol, including screening tests and evaluations, written informed consent will be obtained from the subject in accordance with local practice and regulations. Whenever possible, the investigator(s) will also be involved in this procedure. The background of the proposed study and the benefits and risks of the procedures and study will be explained to the subject. A copy of the informed consent document signed and dated by the subject will be given to the subject. Confirmation of a subject's informed consent will be documented in the subject's medical records prior to any testing under this protocol.

### **Avoidance of Coercion**

It will be made clear to all patients that they can receive transplantation therapy (contingent on their medical suitability) without participation in this trial.

## **STUDY TIMELINES:**

We expect the total duration for this study not to exceed 2 years from the date of the last subject's enrollment. Each individual subject will be part of the study for 12 months after transplantation.

## **STUDY ENDPOINTS:**

### **Primary endpoints:**

One of the 2 primary end points Kidney transplant function assessed as kidney injury markers in urine samples collected at 12-hour and 24-hour trough levels and 2-hour peak levels at 2nd week, 3rd month, 12th month post transplantation, and at any for-cause biopsy event. The injury markers will be assessed using Myriad-RBM KidneyMAP panel <https://myriadrbm.com/products-services/humanmap-services/kidneymap/>.

The other primary end point is immune activation assessed through serial flow cytometric immunophenotyping for immune cells including T and B cell subpopulations as well as donor-reactive TCR repertoire analysis in biopsy, blood and urine.

### **Secondary endpoints:**

Kidney biopsy will be performed per SOC at month 3 and 12 post-transplant. Biopsies will be evaluated and compared between two groups for CNI-related toxicities. Correlations

*Northwestern University Feinberg School of Medicine:* Extended-Release Tacrolimus Vs. Twice-Daily Tacrolimus

between kidney injury markers and biopsy data at 3 and 12 months post-transplant will be performed (details are below).

Antibody responses and correlation with CNI exposure by SOC donor specific antibody (DSA) assessment at months 3 and 12 post-transplant (performed at the Clinical Immunology Laboratory of the CTC).

## **PROCEDURES INVOLVED:**

### **Study Design:**

**Donors:** Blood samples (50ml) from donor subjects will be obtained before transplantation. These donor leukocytes will be used as stimulator cells in studies of functional activity of recipient T-cells. These samples will be processed in the research laboratory of co-investigator, [name].

**Renal Transplant Recipients:** All recipients will receive the same induction immunotherapy at the time of transplant.

#### **Mycophenolate (MMF, Myfortic®)**

The MPA/Myfortic will be initiated at 720- 1250 mg BID orally. The first dose will be given, per SOC. The agent will be given in an open label fashion. Once discharged from the hospital, the subject will obtain this medication via a prescription at a pharmacy of their choice.

#### **Alemtuzumab (Campath-1H®)**

One dose will be 30mg given IV, and administered intra-operatively during renal transplantation. The agent will be given in an open label fashion and will only be administered in the hospital.

#### **Corticosteroids**

Intravenous corticosteroids (prednisolone, Solumedrol®)

##### **Time: Dose**

Preop (Intraop) 500mg

POD#1 250mg

POD#2 125mg

No further steroids will be given post-transplant unless indicated by the following medical conditions: acute renal allograft rejection, renal diseases necessitating the use of steroids, and other systemic diseases such as rheumatoid arthritis (RA), systemic lupus erythematosus (SLE), and asthma.

#### **Tacrolimus (Progra®)**

Tacrolimus will be given 1-2 mg BID, per SOC. The dose will be modified to achieve 12 hour trough concentrations of 8-12 ng/ml. The agent will be given in an open label fashion. Half of the study subjects (randomized; n=25) will be on this drug treatment

#### **LCP-Tacrolimus/Envarsus® XR (Study related drug)**

LCP-Tacrolimus/Envarsus® XR a new once-daily formulation of tacrolimus, was approved by the FDA in 2015 for conversion from twice-daily tacrolimus (above) in kidney transplant recipients. It is a prolonged-release tacrolimus formulation, utilizing a MeltDose drug delivery technology designed to improve the bioavailability of drugs with low water solubility. The other half of the study subjects (randomized; n=25) will be on this drug treatment. LCP-Tacrolimus/Envarsus XR will be given 5 mg QD to achieve a 24-hour trough concentration of 8-12 ng/ml.

[figure not shown]
*Northwestern University Feinberg School of Medicine:* Extended-Release Tacrolimus Vs. Twice-Daily Tacrolimus

### Study Drugs

None of the drugs given in conjunction with this study are provided by the study sponsor, including LCP-tacro/Envarsus XR.

### Recipient Samples collection:

Blood, urine and biopsies will be collected from the kidney transplant recipients as shown in **Figure 2** (bottom).

### Kidney transplant function:

For subjects receiving Standard Tacrolimus + MMF urine samples will be collected at 12-hour trough levels and 2-hour peak levels at 2nd week, 3rd month, 12th month post transplantation, and at any for-cause biopsy event.

For subjects receiving LCP-Tacrolimus/Envarsus XR + MMF, urine samples will be collected at 24-hour trough and 2-hour peak levels at 2nd week, 3rd month, 12th month post transplantation, and at any for-cause biopsy event.

Urine will be used for the analysis of kidney injury markers using Myriad-RBM KidneyMAP panel <https://myriadrbm.com/products-services/humanmap->

Northwestern University Feinberg School of Medicine: Extended-Release Tacrolimus Vs. Twice-Daily Tacrolimus

[services/kidneymap/](#). [The samples will be used also for TcR repertoire analysis; (please see below).]

**Blood Immunophenotyping.**

The approach will be to conduct a multi-parameter flow cytometric immunophenotyping of peripheral blood before and at 3 and 12 months post-transplant to analyze cellular changes.

Methods (14-16): Our well-established 5-color flow cytometric analyses is performed using whole blood to delineate the cellular makeup in terms of both percentages and absolute numbers (**Table 1**). RBCs are lysed before flow acquisition. The analysis is for defining the T cell subsets, monocytes and natural killer cells (Tube 2), the B cells

including naïve, transitional, memory and effector-memory subsets (Tube 3) and the dendritic cells including immature, monocyteoid and plasmacytoid fractions (Tube 4).

**Table 1: Whole blood immunophenotyping panel**

Tube 1	Tube 2	Tube 3	Tube 4
IgG-FITC	CD4-FITC	CD38-FITC	CD3, 14, 16, 19, 20, 56 FITC
IgG-PE	CD14-PE	IgD-PE & IgM-PE	CD33-PE
IgG-ECD	CD56-ECD	CD19-ECD	HLA-DR-ECD
IgG-PC5	CD3-PC5	CD27-PC5	CD11b-PC5
IgG-PC7	CD8-PC7	CD24-PC7	CD123-PC7

In addition to the whole blood analyses, PBMC are isolated from heparinized 40 cc blood samples by Ficoll-Hypaque gradients. Surface markers are identified with indicated monoclonal antibodies, and after fixation and permeabilization the intracellular protein ligands are detected with antibodies shown on the bottom row (**Table 2**). This panel delineates expression of markers for activated, effector, memory, anergic and exhausted cell fractions as well as myriad sub-sets of regulatory T and B cells.

[figure not shown]
**Table 2: Immunophenotyping in using isolated PBMC (surface and intracellular)**

Tube 5	Tube 6	Tube 7	Tube 8	Tube 9	Staining
CD4-ECD	IgD/M-PE	CD3-ECD	CD49b FITC	KLRG-1 PE	Surface
CD25-PC5	CD19-ECD	CD28-PC5	LAG-3 PE	PD1-ECD	
CD127-PC7	CD27-PC5	CD8-PC7	CD4 ECD	CD3-PC5	
CTLA4-FITC	CD24-PC7	CD45RA -FITC		CD8 -PC7	
FoxP3-PE	IL-10 -FITC	FoxP3-PE	FoxP3 PC5 & IL10 PC7	Ki-67 FITC	Intra-cellular

**Donor-reactive TCR repertoire analysis** The approach will be to identify and estimate the total T cell clonal repertoire that a patient is capable of mounting against the donor by performing MLR and purifying reactive cells followed by ImmunoSEQ analysis (17) prior to transplant. Then after transplant, monitor for the absence, presence or amplification of the pre-identified T cell clones in the post-transplant biopsies, blood and/or urine samples. This is a novel innovative technology that we have developed for profiling recipient's immune status against the donor to correlate with the status of the graft. The methodological approach is follows:

Northwestern University Feinberg School of Medicine: Extended-Release Tacrolimus Vs. Twice-Daily Tacrolimus

**Selection of donor-reactive T cells:** Recipient pre-transplant peripheral blood mononuclear cells (PBMC) will be labeled with CFSE dye and then stimulated with PKH266-labeled donor irradiated PBMC in MLR. After 7 days, the proliferating responder cells that have diluted the CFSE are flow-sorted (at NU Flow Core) as shown in **Figure 3** (top middle). Based on previous results, it is expected that the proliferating cells will be >90% CD3+ T cells, distributed into CD4+ or CD8+ cells, with minimal contamination with CD19+ B cells or CD14+ monocytes but some CD56+ NK cells. Both the CD3+CD4+ and

[figure not shown]

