**Figure 3. Flow Sorting and phenotypic subset analysis of donor reactive clones.**  
Bulk MLRs were prepared and the cellular makeup of responder cell populations were delineated after 7 days in culture using fluorochrome coupled monoclonal antibodies. The cells were analyzed first by gating on lymphocytes and then after gating on CFSE diluted proliferating responder cells. The CFSE diluted donor reactive T cells were sorted for ImmunoSEQ analysis.

CD3+CD8+ cell subsets are sorted out separately and is shipped to Adaptive Biotechnologies in Seattle.

**ImmunoSEQ analysis of donor-reactive T cells:** At Adaptive Biotechnologies total genomic DNA is purified from the flow-sorted CD3+CD4+ and CD3+CD8+ cell subsets from each culture using Qiagen DNeasy Blood extraction Kit following the manufacturer's protocol. Then, a multiplex PCR assay that is capable of specifically amplifying rearranged TCRB genes from a complex background followed by deep sequencing is performed (**Figure 4**).

The data is analyzed measuring clonality, proportion and diversity of the T cell repertoire (18-20). These represent the total T cell repertoire the recipient is capable of reacting to the donor. We have denoted the performance of the pre-transplant MLR, isolation of donor reactive clones and ImmunoSEQ analysis, collectively as **AlloSEQ**.

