## ***Enumeration of donor reactive T cell clones in post-transplant kidney biopsies, blood and urine:***

[figure not shown]
The transplant biopsy represents a sampling of the allograft and rejection is manifested as cellular infiltration, mostly of donor reactive T cells and B cells, classically detected through immunohistopathological staining and microscopic examination. An alternate approach that we have developed is to monitor the graft for infiltrating donor-reactive clonotype identified through AlloSEQ (17). This would entail isolation of total genomic DNA from the biopsies, performance of immunoSEQ analysis as above and monitoring for the presence and copy number of donor-reactive clones identified through the pre-transplant AlloSEQ, and then correlating with the severity of rejection monitored through immunohistopathological examinations.

We had proposed that transplant rejection can more easily be diagnosed through the sampling of the urine pellet or peripheral blood for clonal frequency and abundance of donor-reactive T cells pre-identified through AlloSEQ. This is to monitor rejection in a non-invasive manner.

We have already established the technology (17) and other investigators have used it to show that donor reactive clones are reduced or deleted in tolerant kidney transplants (21). Therefore, these proposed studies monitoring post-transplant graft rejection or its absence can be greatly leveraged to innovatively assess the relative efficacies of the drugs being compared.

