For the primary objective, we hypothesize that subjects receiving LCP-Tacrolimus/Envarsus® XR will exhibit significantly greater graft function and lower frequency / abundance of AlloSeq pre-identified donor-reactive T cell clones in the graft, peripheral blood and /or urine at 3 and 12 month post-transplant as compared to the standard of care tacrolimus group. A variety of covariance structures (first order regressive, compound symmetry, Toeplitz, variance components, unstructured) will be carefully examined and compared using the best fitting statistics, such as Akaike's Information (AIC) and Bayesian Information Criteria (BIC). These statistics are likelihood functions and can be compared across models. If, in spite of randomization, distributions of subjects' baseline characteristics are found to be different between the two experimental groups, these variables will be entered as covariates in the statistical analysis.

For the secondary endpoints, we will use logistic regression, Kaplan-Meier method, and Cox proportional hazards models to analyze time-to-event outcomes (acute rejection, graft failure, and death). For allograft immunohistopathology outcomes, we will first develop a comprehensive immune profile of each participant by longitudinal analysis of frequency of T and B cell subsets and function. We will examine how these correlate with immunohistopathology and alloantibody production using Pearson or Spearman correlations. We will compare correlation coefficients between the two experimental groups using Z -tests to determine the distinct effects of each treatment arm. We will also compare the trajectory changes in cell populations and antibody production over 3 and 12 months using both repeated measures ANOVA and random mixed effect models. All tests will be

*Northwestern University Feinberg School of Medicine:* Extended-Release Tacrolimus Vs. Twice-Daily Tacrolimus

two-sided, and an error rate of  $\alpha <0.05$  will be considered statistically significant. All data analyses will be performed using SAS 9.2 statistical software (SAS Inc., Cary, NC).

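### The between-arm comparison of donor-reactive clones does not pre-specify each patient's pre-transplant list length as a covariate, so avoidable noise may stay in a primary endpoint (low priority)

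*Combined protocol and SAP*

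**What the plan says.** The Donor-reactive TCR repertoire analysis section sets out to "identify and estimate the total T cell clonal repertoire that a patient is capable of mounting against the donor". Each recipient's pre-transplant cells are cultured for 7 days against their own donor's cells, the proliferating CD4 and CD8 cells are sorted, and each sort is sequenced. Of the result, the ImmunoSEQ section says "These represent the total T cell repertoire the recipient is capable of reacting to the donor".

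After transplant the same section plans to "monitor for the absence, presence or amplification of the pre-identified T cell clones in the post-transplant biopsies, blood and/or urine samples", so samples are searched only for the clones on that list. In biopsies this means "monitoring for the presence and copy number of donor-reactive clones identified through the pre-transplant AlloSEQ"; in urine or blood the readout is "clonal frequency and abundance of donor-reactive T cells pre-identified through AlloSEQ".

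The readout has primary status. Primary endpoints includes "donor-reactive TCR repertoire analysis in biopsy, blood and urine", and the primary hypothesis in Statistical analysis is that the once-daily arm will show "lower frequency / abundance of AlloSeq pre-identified donor-reactive T cell clones in the graft", peripheral blood and/or urine at 3 and 12 months.

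The only covariate rule, in the same section, is conditional: baseline characteristics enter the model if their distributions turn out to differ between the arms despite randomization. List length is not named. No section fixes the number of clones, divides by list length, or gives a denominator for frequency.

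**The concern.** The list acts as a patient-specific ruler. An unlisted clone cannot score, so of two patients with the same post-transplant alloreactivity, the one with the longer list has more opportunities to register signal. Lists can be expected to differ in length. Each recipient is tested against a different donor, donors are living or deceased, no eligibility criterion concerns HLA mismatch, and no cell input or clone number is fixed. A 7-day culture followed by sorting yields a sample of the reactive repertoire, as the plan's own word estimate concedes, even though the result is then treated as the total.

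If list length drives part of the between-patient spread in abundance, that spread widens the interval for the arm difference in a trial of 25 per arm. List length is fixed before the study drug can act, so it is a legitimate adjustment variable, and the planned sequencing already yields it. The conditional rule does not use it well: it leaves the noise in place when the arms happen to be balanced, and it makes the choice of covariates depend on the data.

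**Working it through.** **The plan's own figure.** Sample size and power gives 0.99 for immune activation (clonal repertoire change) at effect size 2.0, 25 per arm, two-sided alpha 0.05. A noncentral-t calculation gives more than 0.999, both at 25 per arm and at 22 per arm (25 less 10% attrition is 22.5, rounded down). The stated value is safe. No standard deviation is given behind the 2.0.

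**Is list length handled anywhere?** The covariate rule acts only on observed imbalance. The transformation rule in Statistical analysis follows the raw data distribution, not list length. The ImmunoSEQ section computes clonality, proportion and diversity of the pre-transplant list, but no section carries them into the arm comparison. So it is not handled explicitly.

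**Size (assumed inputs).** Let s be the SD of log list length, b the slope of log abundance on log list length, and 1.0 the residual log-SD. None of these is in the documents. Then:

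- Share of variance: R² = b²s² / (b²s² + 1).
- Interval width after adjustment relative to before: √(1 − R²).
- Power is taken at 22 per arm for the difference that has 80% power unadjusted (d = 0.865). After adjustment d becomes 0.865 / √(1 − R²).

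The values s = 0.5, 0.75 and 1.0 correspond to 10th-to-90th percentile spreads of exp(2 × 1.2816 × s) = 3.6-, 6.8- and 13-fold.

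| slope b | R² (s = 0.5 / 0.75 / 1.0) | interval narrower by | power, from 80% |
|---|---|---|---|
| 1 | 20 / 36 / 50% | 11 / 20 / 29% | 88 / 94 / 98% |
| 0.5 | 6 / 12 / 20% | 3 / 6 / 11% | 82 / 85 / 88% |
| 0.25 | 1.5 / 3.4 / 5.9% | 1 / 2 / 3% | 81 / 81 / 82% |

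Example, b = 0.5 and s = 1.0: R² = 0.25 / 1.25 = 0.20; √0.80 = 0.894, so 11% narrower; d = 0.865 / 0.894 = 0.967, power 0.88.

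**Cost of estimating the slope.** With k covariates and 44 patients, chance imbalance in the covariates inflates the expected variance by about 1 + k/(44 − k − 3) (normal covariates). This is 1 + 1/40 = 1.025 for one and 1 + 2/39 = 1.051 for two, or about 1.2% and 2.5% in width. If list length explained nothing, power would go from 0.80 to about 0.79 with one covariate and 0.78 with two. So at slope 0.25 the gain and the cost roughly cancel; at slope 1 the gain clearly dominates.

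**At the plan's effect size.** Take 2.0 as the effect net of list length, and let list length carry a share of the variance. The unadjusted effect is 2.0 × √(1 − share). At 22 per arm, a share of 0.2 / 0.4 / 0.6 gives 1.79 / 1.55 / 1.26 and power above 0.999 / 0.999 / 0.984. With a true effect of 1.0 the same shares give power of 0.83 / 0.71 / 0.54, against 0.90 with no such noise.

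**Validity.** In a simulation with slope 1, 22 per arm and 20,000 replicates, type I error was about 0.05 with and without adjustment. At effect 1.0 and list-length coefficient of variation 1.0, power was 0.70 unadjusted and 0.89 adjusted.

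**The case against.** The case against has real force.

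- **The slope is unknown.** Copy number and abundance can be dominated by a few large clones, so a longer list may mostly add rare ones. In one illustration (assumed power-law clone sizes, list filled largest first), lengthening the list from 1,000 to 10,000 clones raised summed abundance only 1.02- to 1.31-fold. This stands, and it is why the table goes down to slope 0.25.
- **The plan's effect size is 2.0.** At that size there is almost no power to recover. This stands too. What remains is interval width, which still matters in a self-described pilot, and protection if the true effect is nearer 1.0.
- **The conditional rule could cover chance imbalance.** It could, if list length is counted as a baseline characteristic. It does not address within-arm noise when the arms are balanced.
- **The metric is not fully defined.** If repertoire change means within-patient change on one list, much of the length effect could cancel, but no pre-transplant sequencing of unsorted blood is described to serve as that baseline. If frequency means the share of listed clones detected, length is partly handled, but the plan does not say so.
- **The cited method paper may standardise cell input.** That cannot be checked from these documents.

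A reader might infer something stronger: that unequal lists bias the arm comparison, or that a tenfold longer list brings a proportionate rise in signal and hence a large loss of power. The documents support neither. The list is set before transplant and the arms are randomised, so there is no systematic tilt, and no list lengths or slope are given.

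**Conclusion.** The point holds as a matter of precision. Each patient's post-transplant signal is scored against a list of that patient's own length, and the plan neither adjusts for that length nor commits to doing so; its covariate rule waits for an observed imbalance. There is no bias and no inflation of type I error.

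The size is unknown. It rests on three assumptions outside the documents: the spread of list lengths, the residual spread, and above all the slope. Across the range examined, the benefit runs from a substantial narrowing of the interval to essentially nothing once the cost of estimating the slope is charged. On the plan's own planning effect, the conclusion of the test would hardly change. This is a cheap improvement of low priority, not a flaw that threatens the primary comparison.

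**What to change.** In Statistical analysis, next to the primary hypothesis, add a sentence to this effect: the log number of unique clones on the patient's pre-transplant AlloSEQ list (CD4 and CD8 lists) is a covariate in every between-arm comparison of donor-reactive clones, whether or not the arms differ on it. Use a covariate rather than dividing by list length, because length may carry real biology.

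In the same place, state the denominator of frequency (for example all sequenced templates, or listed clones), since the role of list length depends on it.

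If the share of listed clones detected is also reported, adjust it for list length too. It is not a length-free check: longer lists hold more rare clones, and in the illustration above the share fell from 0.41 to 0.08 as the list grew from 1,000 to 10,000.

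The cost is a sentence or two, no new assay and no extra patients. The model uses one or two degrees of freedom, with a worst-case loss of about one to two points of power if list length turns out to be irrelevant.
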